The primary outcome variable is percentage of total prescribed medication doses taken as assessed by a 3 day self-report adherence questionnaire. The percentage of total prescribed doses taken will be compared in the two arms with a  $X^2$  test. Prior studies of non-drug abusers have shown that most patients report approximately a 70-80% adherence rate over the week prior to questioning with a standard deviation of around 20[8]. This self-reported adherence rate correlates with an actual adherence rate of around 55% as measured by microelectronic monitoring systems [8]. In other words, patients usually over report adherence by approximately 15-20% in a reproducible manner that still predicts changes in viral load. There is little data looking at self-reported adherence in a drug abusing population. One study has shown however that 32% of drug users obtain a viral load <400 copies/ml compared to 45% of non-users. The approximately 45% virologic response in non-users in this study is similar to the electronically monitored compliance of 55% in the previous study [7]. The lessened virologic response may be a result of pharmocokinetics and pharmocodynamics as well as viral resistance. Therefore, based on prior studies, non-users of drugs are likely to self-report around 70% adherence. Given, the lack of significant data on active drug abusers, 50% self-reported adherence is a reasonable estimate. To detect this difference, 17 subjects in each group are required.

To detect a  $0.9 \log_{10}$  difference in change in HIV-1 RNA viral load at 8 weeks (the time interval it takes to detect a  $1 \log_{10}$  change in viral load according to national guidelines) between groups assuming a standard deviation of 1.5 by unpaired t-test, a sample size of 45 subjects in each arm is required. Change in viral load is defined as the difference in  $\log_{10}$  copies/ml between the value measured at the time of the initial visit and the value at the 8-week visit. In a study comparing drug users and non-users, a  $0.9 \log_{10}$  difference was detected ( $0.8 \log_{10}$  change in the drug users and a  $1.7 \log_{10}$  change in the non-users) [7].

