To compare the proportion of subjects who obtain undetectable HIV-1 RNA viral loads at 16 weeks in the two arms a  $X^2$  test will be performed. In order to have power to detect a 20% difference between groups, assuming 40% will achieve undetectable levels in treatment arm and 20% will achieve undetectable levels in the standard of care arm, 91 subjects are required in each group.

Multiple linear regression analysis of the data will be performed to correlate adherence with other variables including age, gender, ethnicity, percentage of urine samples positive for cocaine during the study, utilization of alternate treatment modalities, and other variables shown to affect adherence in other research such as drug side effects or not being able to meet food and water requirements of the regimen [8b].

Data will be analyzed by an intention to treat analysis.

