#### F. Study Questionnaires

Following is a list of all questionnaires to be used in this study. Please see the appendix for examples of all study instruments.

- 1. The Drug Abuse Screening Test (DAST) An instrument shown to be effective and valid for drug abuse screening [13-15]. With a cut-off level of 6 positive responses on the test, it demonstrates 85% overall accuracy in classifying patients with drug abuse problems as compared to a diagnostic interview for DSM criteria [16].
- 2. The Marlowe-Crowne Social Desirability Scale (SDS)- An instrument used to assess a subject's reluctance to express unpopular beliefs or behavior in order to avoid making a negative impression. Validated as a means of estimating the likelihood that a given subject is over reporting adherence to treatment. [17] To be administered at the end of the study period to all subjects to verify that the social desirability characteristics of the two arms are similar.
- 3. Three Day Adherence Questionnaire (Part A and B) A questionnaire to be filled out by the patient with the assistance of the investigator who will be blinded in regards to the medication regimen that the patient is actually on. The investigator can provide assistance in the form of visual cues (such as photos of pills). This form requires subjects to actually recall their medication regimen to further verify that their statements regarding adherence are accurate. The form also includes some questions for the subject to answer in the event that any doses were missed to assess the reasons for missing doses. [18]

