# Three Day Adherence Questionnaire (Part B)

Check one response for each of the following questions regarding reasons why you missed taking your medication: N=Never, R=Rarely, S=Sometimes, O=Often.

a)	Taking pills didn't fit in with your daily routine?	NRSO
b)	Simply forgot?	NRSO
c)	Too hard to take so many pills according to a schedule?	NRSO
d)	Wanted to avoid side effects?	NRSO
e)	Felt like the drug was toxic/harmful?	NRSO
f)	Did not want others to notice you taking medication?	NRSO
g)	Feel asleep/slept through dose time?	NRSO
h)	Felt sick or ill?	NRSO
i)	Felt depressed/overwhelmed?	NRSO
j)	Ran out of pills?	NRSO
k)	Felt good?	NRSO
l)	Didn't understand regimen?	NRSO
m)	You knew what was best for you?	NRSO
n)	Didn't fit with meals/didn't have water?	NRSO
0)	Didn't feel like taking pills?	NRSO
p)	Were drunk or high?	NRSO

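### Side effects and food/water difficulty are named as predictors of adherence, but the protocol's only items on them ask for reasons for missed doses, so the predictor may depend on the outcome

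*Protocol*

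**What the plan says.** Protocol section B states: "Multiple linear regression analysis of the data will be performed to correlate adherence with other variables including age, gender, ethnicity". The list goes on to cocaine-positive urines, use of other treatment, and variables found elsewhere to affect adherence, with "drug side effects or not being able to meet food and water requirements of the regimen" as the examples. Adherence itself is defined in the same section: "The primary outcome variable is percentage of total prescribed medication doses taken as assessed by a 3 day self-report adherence questionnaire".

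Section F opens with "Following is a list of all questionnaires to be used in this study" and names three: the DAST, the Marlowe-Crowne scale and the Three Day Adherence Questionnaire. Of the third it says that the form includes "some questions for the subject to answer in the event that any doses were missed to assess the reasons for missing doses". Part B, in the appendix, is headed "Check one response for each of the following questions regarding reasons why you missed taking your medication" and is graded Never, Rarely, Sometimes or Often. Item d reads "Wanted to avoid side effects" and item n reads "Didn't fit with meals/didn't have water". Item e asks whether the drug was felt to be harmful.

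In Part A, a subject who reports no missed dose in the three-day chart is sent to question 6, which asks only when a dose was last skipped. Section I describes each subject's data as laboratory, drug-test and questionnaire results.

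**The concern.** A predictor should be measured in the same way whatever the value of the outcome. Here the outcome comes from Part A and the only visible measure of two predictors comes from Part B of the same form, where the questions presuppose a missed dose. A fully adherent subject with troublesome side effects has no natural place to say so. The answer is either blank or 'Never'. A subject with the same side effects who misses doses can score up to 'Often'.

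Item d has a second weakness. It records a motive for missing, not whether side effects occurred, so it does not measure the predictor that section B names.

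At stake is the reading of the regression: side effects and food/water problems could be reported as correlates of poor adherence when they are unrelated to it. This is a matter of what is collected and from whom. A later analysis plan can choose the scoring, but it cannot recover answers that adherent subjects were never asked to give.

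**Working it through.** **No figure to reproduce.** The protocol gives no sample size, power or effect size for the regression. The check traces the predictors to their source and then sizes the artefact under stated assumptions.

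**Step 1: trace the predictors.** The DAST and the Marlowe-Crowne scale contain nothing on antiretroviral side effects or food and water. Part A records drugs, pills, dose frequency and missed doses; question 6 records the last skip. That leaves Part B items d, e and n.

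**Step 2: inputs.**
- From the protocol: 182 subjects (section B); questionnaires every two weeks over 4 months, about 16 / 2 = 8; adherence SD of about 20 percentage points; planning values of 50% and 70% self-reported adherence.
- Assumed: 6 doses per three-day recall (two a day); true side effects in 40% of subjects, independent of adherence; Part B answered only when a dose was missed in the three days; test at two-sided 5%.

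**Step 3: how often the item is forced to zero.** Let each subject's dose-taking probability p follow a beta distribution with mean m and SD 0.20, so that a + b = m(1 − m)/0.20² − 1 and a = m(a + b). The chance that a questionnaire shows no missed dose is E[p⁶], the product over j = 0 to 5 of (a + j)/(a + b + j).
- m = 0.50: a + b = 0.25/0.04 − 1 = 5.25 and a = 2.625. The product is 0.500 × 0.580 × 0.638 × 0.682 × 0.716 × 0.744 = 0.067.
- m = 0.70: a + b = 0.21/0.04 − 1 = 4.25 and a = 2.975. The product is 0.700 × 0.757 × 0.796 × 0.824 × 0.845 × 0.862 = about 0.25.

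So about 7% of questionnaires are forced to 'Never' at 50% mean adherence and about 25% at 70%. These come mainly from the most adherent subjects, which is why the correlation is negative and grows with mean adherence.

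**Step 4: simulated regression of mean adherence on mean item score, with no true association.**

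| Mean adherence | Non-misses scored 'Never': false rejection | Mean r | Mean over answered questionnaires only: false rejection |
|---|---|---|---|
| 50% | about 16% | −0.08 | about 5% |
| 67% | about 74% | −0.20 | about 5% |
| 70% | about 86% | −0.23 | about 5% |

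**Step 5: sensitivity.**
- The last column assumes that the Never-to-Often answer does not depend on how many doses were missed. If the answer rises with that number, false rejection under the same averaging is still about 80%.
- If the 40% prevalence is replaced by a burden spread evenly over scores 0 to 3, 'Never' scoring gives 43% false rejection at 50% adherence and about 100% at 70%.
- If the burden is asked of every subject whether or not doses were missed, false rejection is 4 to 6% and the mean correlation is about 0.

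**The case against.** The strongest reply is that the protocol does not commit the error. Section B gives the two variables as examples and does not say that they come from Part B, which items would be used or how they would be scored. Clinic charts might note side effects. Coding of covariates is commonly left to the SAP. This stands in part: Part B is an inference. But the protocol names no chart extraction, and it has no other source at all for food/water difficulty. If Part B is not the source, the two predictors have no planned measurement and the same remedy applies.

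Second, the restriction to missed doses is not clearly limited to three days. Part B carries no skip instruction of its own, and question 6 covers earlier skips, so a subject with a clean three-day chart might still answer it. This also stands, and the simulated strict restriction may overstate the artefact.

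Third, ordinary scoring can remove it: averaging answered questionnaires restores about 5%. That holds only if the answers are unrelated to the number of doses missed, which is doubtful on a frequency scale about reasons for missing. Leaving non-missers blank excludes few subjects, about 0.1% at 50% adherence and 2.8% at 70%, because almost everyone misses a dose on at least one of 8 questionnaires.

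A reader might go further and infer that a false finding is near certain, or that the cocaine-urine coefficient in the same model is seriously distorted. The documents support neither. The first needs a scoring rule that the protocol does not state. On the second, adding a cocaine variable to a subject-level model with 'Never' scoring moved its coefficient by about 1%, 3% and 4% at 50%, 67% and 70% adherence. Larger shifts appeared when only questionnaires with missed doses were kept, a model that section B does not specify.

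**Conclusion.** The point holds in a limited form. The protocol names two predictors that its own forms do not measure in everyone, and the only items that touch them are tied to missed doses. If those items are used, a spurious negative association with adherence can arise. Its size runs from nominal to large according to scoring, mean adherence and how subjects grade their answers; the figures above rest on the assumed 6 doses, 40% prevalence, independence and three-day restriction.

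The regression is a supporting analysis. The between-arm comparison of adherence and both viral-load comparisons are unaffected, and a material effect on the cocaine-urine coefficient is not shown. The change is worth making because it is cheap and cannot be made once the data have been collected.

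**What to change.** At each two-weekly questionnaire, ask every subject, whether or not a dose was missed, two direct questions: did they have side effects from their antiretrovirals, and did they have difficulty meeting the food and water requirements of the regimen? State in section B that these answers are the regressors. Keep Part B as a description of reasons for missing.

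If the questions are not added, remove the two variables from the regression and report Part B descriptively among questionnaires with missed doses.

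The first option costs two questions in an interview that section C puts at about 15 minutes, plus a sentence in section B. The second costs one sentence and gives up the two predictors.

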#### C. Study Procedure

All subjects participating in the study are to be followed by medical care providers in the outpatient HIV clinic and all medical management will be left to the discretion of those providers. The time intervals chosen in this study for checking viral loads after the initiation of HAART therapy correspond with national treatment guidelines [9]; however additional blood tests are at the discretion of the medical provider. Although it is not possible to blind this study, no data will be shared with either the subjects or their providers. The study period will last 4 months. Study visits will occur once a week for the first 6 weeks and then every 2 weeks thereafter. Subjects in both arms will have a urine dip test to

Columbia University College of Physicians and Surgeons

check for cocaine at every visit which will only take 5 minutes to collect and process. Also, every two weeks the subjects will be asked the questions on the 3-day adherence questionnaire to assess their medication adherence. The questionnaire will take about 15 minutes at these visits. The urine samples and questionnaires will be completed with an investigator in the HIV outpatient clinic prior to any medical visit that subject might have that day. The subjects in the treatment arm will have therapy sessions in the addiction medicine research clinic on the same days as their other study activities. All subjects will receive compensation for coming to the scheduled visits and providing urine samples in the form of vouchers. They will receive a \$15 voucher at each visit in the form of subway fare (Metrocard) or a voucher to a local fast food chain. If they complete the study and come to all of the scheduled visits, they will receive a \$50 gift certificate to Old Navy.

At the first visit, informed consent will be obtained and the study will be explained to the patient by one of the investigators. Also, the primary medical provider will initiate HAART therapy. Because adherence to the prescribed regimen is the primary outcome, patients may be placed on any of the "strongly recommended" regimens according to current national guidelines [9] at the discretion of the primary medical provider as long is the regimen is a class sparing regimen. (e.g. NNRTI-sparing, PIsparing or a PI- and NNRTI-sparing regimen) The medical care provider will choose a regimen at the first study visit while still blinded to which arm of the study the patient is in to avoid biasing the choice.

The treatment intervention is cognitive behavioral therapy aimed at relapse prevention and coping skills training. It is an entity well described in psychiatric literature as an effective means of treating cocaine addiction. Cocaine addiction is being targeted in this study because it has a high prevalence amongst HIV positive patients and because it is not associated with a physical withdrawal syndrome upon cessation that would require detoxification. The treatment is essentially a problem-solving process and a reorientation of life attitudes consisting of psychotherapy, self-observation and monitoring, homework assignments, the use of guided imagery and role-play and bibliotherapy [10]. The therapy will have a "boost" period of visits every week followed by visits every two weeks thereafter. Psychotherapists trained in addiction treatment and this type of therapy will give the treatment. One review of 25 randomized trials looking at this relapse prevention therapy across all substances found that it was more effective than no treatment at enhancing the durability of cessation attempts and decreasing the severity of relapses [11].

Although many techniques for measuring adherence have been tried, all of them have been correlated with patient self-assessment questionnaires with good reproducibility. Self-assessment questionnaires have been compared to measuring serum antiretroviral drug levels [4], electronic monitoring (MEMS) caps [8], and provider-reported adherence [12] with similar correlations between HAART medication adherence and virologic and immunologic markers. Self-assessment questionnaires have many advantages over these other methods in that they are inexpensive, simple to administer, and do not require patients to follow complicated instructions.

#### **D.** Study Drugs

There are no study drugs included in this protocol. All antiretroviral therapy to be used is FDA approved and will be prescribed according to accepted national treatment guidelines.

#### E. Medical Devices

The HIV-1 RNA-PCR assay by Roche is the recommended assay for guiding patient treatment according to current national guidelines and is FDA approved for this purpose [9]. The urine dip-stick test is likewise a widely used and FDA approved means of tracking cocaine use via a urine test. There are not experimental or investigational medical devices included in this protocol.

#### F. Study Questionnaires

Following is a list of all questionnaires to be used in this study. Please see the appendix for examples of all study instruments.

- 1. The Drug Abuse Screening Test (DAST) An instrument shown to be effective and valid for drug abuse screening [13-15]. With a cut-off level of 6 positive responses on the test, it demonstrates 85% overall accuracy in classifying patients with drug abuse problems as compared to a diagnostic interview for DSM criteria [16].
- 2. The Marlowe-Crowne Social Desirability Scale (SDS)- An instrument used to assess a subject's reluctance to express unpopular beliefs or behavior in order to avoid making a negative impression. Validated as a means of estimating the likelihood that a given subject is over reporting adherence to treatment. [17] To be administered at the end of the study period to all subjects to verify that the social desirability characteristics of the two arms are similar.
- 3. Three Day Adherence Questionnaire (Part A and B) A questionnaire to be filled out by the patient with the assistance of the investigator who will be blinded in regards to the medication regimen that the patient is actually on. The investigator can provide assistance in the form of visual cues (such as photos of pills). This form requires subjects to actually recall their medication regimen to further verify that their statements regarding adherence are accurate. The form also includes some questions for the subject to answer in the event that any doses were missed to assess the reasons for missing doses. [18]

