# Three Day Adherence Questionaire (Part A)

**Note**: The chart below should be customized to the client's antiretrovirals. Steps 1-3 should be generated interactively with the client, and should be an accurate representation of the client's current drug regimen. Please use prompts or visual aids if necessary to complete the table with the client. Please fill in"dk" for don't know if patient is unable to fill in an area of the chart.

Step 1 Names of antiretroviral drugs	Step 2 # pills taken at each dose	Step 3 # times dose is taken per day	Step 4 # doses missed Yesterday	Step 5 # doses missed 2 days ago	Step 6 # doses missed 3 days ago
1)					
2)					
3)					
4)					
5)					

If there were no reported missed doses in the chart above, please ask the following questions:

- 6. When was the last time you skipped any of your medications?
  - a. never skip medications
  - b. more than two weeks ago
  - c. 1-2 weeks ago
  - d. within the past week

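### The primary outcome is a percentage of prescribed doses, but the form takes the regimen from the subject's recall, with an interviewer blind to the prescription and no check against it

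*Protocol*

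**What the plan says.** Protocol section B defines the endpoint: "The primary outcome variable is percentage of total prescribed medication doses taken as assessed by a 3 day self-report adherence questionnaire". The denominator is therefore what was prescribed, and the three-day form is the only stated source of data.

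Section F, item 3 says the form is filled in by the subject with the help of "the investigator who will be blinded in regards to the medication regimen that the patient is actually on". It presents this as a safeguard: "This form requires subjects to actually recall their medication regimen to further verify that their statements regarding adherence are accurate". Visual cues such as pill photographs are allowed.

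The appendix form (Part A) opens with a different instruction: "The chart below should be customized to the client's antiretrovirals". It goes on: "Steps 1-3 should be generated interactively with the client, and should be an accurate representation of the client's current drug regimen". Steps 1 to 3 are drug names, pills per dose and times per day. Steps 4 to 6 record missed doses in the same rows, so only for drugs that have been listed. The entry dk is provided "for don't know if patient is unable to fill in an area of the chart".

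The true regimen is known elsewhere. Under section C, "The medical care provider will choose a regimen at the first study visit".

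**The concern.** The endpoint needs the number of doses prescribed over three days. The form collects only the number the subject remembers being prescribed. The two agree when recall is complete. When it is not, the form gives a percentage of recalled doses, which is a different quantity.

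The two instructions to the interviewer also pull apart. Section F keeps the interviewer ignorant of the regimen, while the Part A note asks for a chart that represents it accurately. Staff who follow section F and staff who follow Part A could arrive at different denominators for the same subject. What is at stake is the meaning of the primary endpoint and, if recall differs by arm, the primary comparison.

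**Working it through.** **The plan's own figure.** Section B states 17 per group for 70% against 50% with a standard deviation of about 20. A two-sample t-test with two-sided 5% significance and 80% power (both assumed, since the protocol states neither) gives 16.7, so 17. That figure reproduces and is not in dispute. The question is how each subject's score is built.

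**Where the denominator can come from.**
- Section B requires prescribed doses.
- Part A yields drugs listed × recalled times per day × 3 days.
- Section F says recall serves as verification, but neither section F nor Part A sets the recalled regimen against the prescription.
- When no misses are reported, Part A asks when a dose was last skipped. That does not restore an unlisted drug to the denominator.

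**Single-subject arithmetic.** The protocol fixes no regimen, so assume three drugs twice daily: 3 × 2 × 3 = 18 prescribed doses.

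| Situation | Form | Prescribed basis |
|---|---|---|
| One drug untaken and unlisted, the others fully taken | 12/12 = 100% | 12/18 = 67% |
| Two drugs untaken and unlisted, the third fully taken | 6/6 = 100% | 6/18 = 33% |
| All drugs recalled and taken once daily, no misses reported | 9/9 = 100% | 9/18 = 50% |
| One drug fully taken but unlisted, 2 of 12 listed doses missed | 10/12 = 83% | 16/18 = 89% |
| All doses taken, frequency recalled as three times daily, the extra 9 doses reported missed | 18/27 = 67% | 18/18 = 100% |

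The first three rows overstate adherence and the last two understate it.

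**Effect on the mean level.** Let a be adherence on the listed drugs when one untaken drug of three is omitted. The form gives a and the prescribed basis gives 2a/3, so the overstatement is a/3. Take a from section B's 50% and 70%:
- 50/3 = 16.7 points and 70/3 = 23.3 points per affected questionnaire.
- If 10 to 20% of questionnaires are affected (an assumption, as the documents give no rate), the range runs from 0.10 × 16.7 = 1.7 to 0.20 × 23.3 = 4.7 points.

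**Effect on the comparison.** Suppose the form shows 70 against 50, a difference of 20. With omission shares p and q in the treatment and standard of care arms, the difference on the prescribed basis is 70(1 − p/3) − 50(1 − q/3):
- p = q = 20%: 65.3 − 46.7 = 18.7. The form overstates the difference by 1.3 points.
- p = 0, q = 20%: 70 − 46.7 = 23.3. The form understates it by 3.3 points.
- p = 20%, q = 0: 65.3 − 50 = 15.3. The form overstates it by 4.7 points.

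**Effect on power.** Now take 70 and 50 as the true means, with omission only in the standard of care arm, scores there multiplied by 1.5 (50 becomes 75) and the standard deviation held at 20:
- 20% omission: 0.8 × 50 + 0.2 × 75 = 55. The scored difference is 15 and power at 91 per arm is 99.9%.
- 50% omission: 0.5 × 50 + 0.5 × 75 = 62.5. The scored difference is 7.5 and power is about 72%.

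**The case against.** The best defence is that section B already says prescribed doses, that the provider's prescription exists, and that calling recall a verification implies some later comparison. Scoring of unlisted drugs and dk cells could sit in a statistical analysis plan that is not shown. Pill photographs help a blinded interviewer, and the accuracy sentence may be only an aim. Over-reporting is acknowledged in section B, and viral load gives an objective check.

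Part of this stands. The absence of a detailed scoring rule is not in itself a fault of the protocol, and the photographs will reduce omissions. But a photograph cannot tell a blinded interviewer that a drug is missing from the list, and an implied comparison is not a stated one. The conflict between section F and Part A lies within this document. General over-reporting is also a different matter from a denominator that changes with recall.

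A reader might infer more than the documents support:
- *That the error always raises adherence.* The last two rows of the table show otherwise.
- *That it is largest in the least adherent.* A subject who takes nothing and reports it scores 0/12, the same as 0/18.
- *That the mean is overstated by 3.3 to 6.7 points, close to the roughly 8.4 points detectable at 91 per arm.* The first figure (33.3 × 10 to 20%) requires perfect adherence on every listed drug. The comparison also sets a shift in level against a between-arm difference.
- *That a real benefit is probably hidden.* This needs more omission in the standard of care arm, and the documents give no information on that.

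**Conclusion.** The point holds as a mismatch between the defined endpoint and its instrument, together with a contradiction between section F and the Part A note. Followed as written, the form can return 100% for a subject at 67% on the prescribed basis (three drugs twice daily, one untaken and unlisted, both assumed). The plausible overstatement of the mean is about 1.7 to 4.7 points. That rests on 50 to 70% adherence on the listed drugs and an assumed 10 to 20% of questionnaires omitting one untaken drug of three.

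The between-arm comparison is materially affected only if omission differs by arm. Its size and direction cannot be determined from the protocol. The change is worth making because this is the primary endpoint and the remedy is cheap.

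**What to change.** 1. Take the denominator from the regimen in the clinic record for the three recalled days, matched to the form after the interview by someone other than the interviewer. The interviewer can then stay blind.
2. Prespecify one rule for a prescribed drug that is not listed, or that has dk in the frequency or missed-dose cells. One option is to count it as not taken, with a sensitivity analysis treating it as missing. The sensitivity analysis matters because the first rule can confuse poor naming with non-adherence, and so favour whichever arm knows its regimen better.
3. Do not count dk for pills per dose as a missed dose, since that cell does not enter the dose count.
4. Reword section F, item 3 and the Part A note so that they agree on what the interviewer knows and on where accuracy is established.

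The cost is copying the regimen from the chart at each questionnaire date, plus the wording changes. No visits are added.
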